7.3.2.2. Serious Adverse Events

Serious adverse events or serious adverse drug reactions are undesirable medical incidents as follows:

- If a death is caused;
- If it is life-threatening (risk of an immediate death);
- If hospitalization or extended duration of hospitalization is required;
- If persistent or significant disability or malfunction is induced (substantial disruption in the ability to conduct normal life functions);
- If congenital anomalies/birth defects are induced.

If lack of efficacy is related to any serious adverse event, the lack of efficacy should be reported as an adverse event.

Medical and scientific judgment should be exercised in determining whether or not an adverse event is a significant medical event. A significant medical event may not be immediately life-threatening, or result in death or hospitalization. However, if it is determined that the event may jeopardize the study subject or may require intervention to prevent one of the outcomes as defined as above, it should be reported as a serious adverse event.

Examples of such events include allergic bronchospasm requiring intensive care in the emergency room or at home, blood dyscrasia or convulsions that do not result in hospitalization, or development of drug dependency or drug abuse.

Hospitalization

Hospitalization is defined as all initial admission to the hospital or health facility equivalent to the hospital (including admission for less than 24 hours) or extended duration of the existing hospitalization. Hospitalization also includes the transition to the acute/intensive care unit within the hospital (e.g. from psychiatry to the internal medicine ward, from the internal medicine ward to the cardiovascular disease intensive care unit, or from neurology to the tuberculosis unit). Emergency room visits do not necessarily mean hospitalization, but the event that causes the emergency room visit should be evaluated for its medical significance.

When adverse medical events do not occur, hospitalization itself cannot be seen as an adverse event and should not be reported. For example, the following hospital admission involving no adverse events is not reported:

- Social hospitalization (e.g. the study subject has no place to stay)
- Administrative hospitalization (e.g. for annual periodical medical examination)

- Optional hospitalization that is not related to any sudden medical adverse events (e.g. for plastic surgery chosen by the subject)
- Hospitalization for observation that involves no medical adverse events
- Hospitalization to treat the existing condition that is not related to the manifestation of a new adverse event, or the deterioration in the existing condition (e.g. for complete medical examination of abnormal laboratory test results before continuing treatment)
- Hospitalization according to the protocol during the clinical trial (e.g. for the procedure required by the study protocol)

7.3.2.3. Collection of Adverse Event Data

All the adverse events observed in the post-marketing surveillance or reported voluntarily are recorded, regardless of the dose groups (if applicable) or suspicion of the causal relationship with Xyntha Solofuse prefilled syringe, on the adverse event report page of the case report form (CRF) as follows:

For all the adverse events, the investigator must collect adequate data both to determine outcomes of the adverse events and to assess whether or not the adverse events meet the criteria for the serious adverse event that should be reported immediately to Pfizer or its representative (see Section “Serious Adverse Events”). For all the adverse events, the investigator must collect sufficient data to determine the causality. The investigator should determine the causality of the adverse events. For the adverse events that have a causal relationship with Xyntha Solofuse prefilled syringe, follow-ups by the investigator are required until the event or its sequela resolves or stabilizes at a level acceptable to the investigator, and until it corresponds with Pfizer’s opinion on that assessment.

7.3.2.4. Laboratory Test Data

Laboratory tests do not have to be conducted because this study is a non-interventional study. After the investigator conducts laboratory tests for diagnosis and monitoring by methods of general medical practice, the results can be collected. First, indicate whether the test was conducted by marking with either “Not tested” or “Tested”.

- Test Items: Record the items for which abnormal test measurements have been found.
- Normal value range (unit): Record the normal range of the relevant institution with the unit for each item entered.
- Date of Test: Record in the order of year/month/day.
- Pre-dose/post-dose: Record the test measurements.

If “Tested” is marked, check “Yes”, “No” or “Not tested during drug administration” to indicate if there has been a clinically significant abnormality after drug administration

compared to before drug administration. If “Yes” is checked, record details for the following items:

See Section 7.3.2.1 to decide if the clinically significant abnormality should be reported as an adverse event. If it meets the pertinent criteria, it should be recorded in the adverse event section of the case report form.

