7.7.2.1. Safety Analysis

- Number and incidence of adverse events sorted by body organ, disease/symptom
- If the data are adequate, the Chi-square test (X^2 -test) or the Fisher's exact test can be used for subgroup analysis.

If necessary and if the data are adequate, the pairwise comparison and/or the descriptive analysis method will be used for clinically significant abnormalities found in the laboratory tests that have been reported as adverse events.

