 - Not related to this medicinal product:
 - IV. Unlikely
- 3) Occurrence status of adverse event by demographics and baseline characteristics
- Occurrence status of adverse events will be presented in frequency and percentage and incidence proportion with 95% confidence interval based on categorical variables of demography and baseline characteristics of the patients (sex, age group, past/present disease status, renal/hepatic disorder status). To identify statistically significant difference in occurrence of adverse events among demography and baseline characteristics, Chi-square test or Fisher's exact test will be performed.
- 4) Occurrence status of adverse event by concomitant treatment/therapy
- Occurrence of adverse events will be presented in frequency and percentage and incidence proportion of adverse events with 95% confidence interval by concomitant treatment status and concomitant therapy status. To identify statistically significant difference in occurrence of adverse events among concomitant treatment status, concomitant therapy status, Chi-square test or Fisher's exact test will be performed.
- 5) Analysis of factors that affect safety
- Logistic regression analysis will be performed and an odds ratio with 95% confidence interval will be presented to identify the factors that affect occurrence of adverse events in demography and baseline characteristics (sex, age group, past/present disease status, renal/hepatic disorder status), or concomitant treatment status, concomitant therapy status, etc.

Statistical Analysis Plan for rPMS

- 6) Test of difference for laboratory data before and after administration.
Laboratory data before and after administration will be presented by descriptive statistics and test of difference for laboratory data before and after administration will be performed by using paired t-test (or Wilcoxon signed-rank test). This analysis will be performed if possible.
- 7) Distribution for special patient populations (children (age<19), elderly (age≥65), renal disorder, hepatic disorder, pregnant woman) will be presented. Also, adverse events and adverse drug reactions collected by these groups will be presented in incidence proportion and number events of it for each SOC and PT.

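### The SAP's paired before/after laboratory tests take no account of the protocol's abnormality-based recording rule, which can bias the estimated change and inflate the type I error

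*Protocol*

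**What the plan says.** Protocol 7.3.2.4 makes laboratory testing optional and starts with a mark for tested or not tested. Where tests were done, the investigator ticks a box "to indicate if there has been a clinically significant abnormality after drug administration" relative to before it; on a yes, the site is to "record details for the following items". The items described in that section are the test item ("Record the items for which abnormal test measurements have been found"), the normal range, the date, and the values ("Pre-dose/post-dose: Record the test measurements").

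Protocol 7.7.2.1 narrows its own laboratory comparison: "the pairwise comparison and/or the descriptive analysis method will be used for clinically significant abnormalities found in the laboratory tests" that were reported as adverse events, if necessary and if the data are adequate.

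SAP 6.6(6) has no such limit. It gives descriptive statistics for laboratory data before and after administration, and a "test of difference for laboratory data before and after administration will be performed by using paired t-test", with the Wilcoxon signed-rank test as the alternative. It adds: "This analysis will be performed if possible". SAP 5.1 sets a two-sided 5% level.

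Two other places list laboratory content. Protocol 7.2.5.1 names blood, biochemistry (including inhibitors) and urine tests among the information recorded for each subject. SAP 4.6(2) names the individual items. Neither says that normal values are entered.

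**The concern.** A paired test holds its level when the pairs are a fair sample of the before/after differences. Here the recording rule appears to keep a pair because of its post-dose value, or because it worsened. Subjects whose values rose by chance past the limit enter the analysis; those whose values fell by chance back within it do not. The mean difference then moves towards worsening even if the drug does nothing.

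The result would be mean changes and p-values in a report to the regulator that suggest laboratory deterioration produced by selection. A related issue touches the primary objective, detection of factor VIII inhibitor: an inhibitor frequency needs the number of subjects assayed, and that requires negative assays to be countable.

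**Working it through.** **Inputs from the documents.** Two-sided 5% level (SAP 5.1); at least 86 subjects with safety data (Protocol 5); recording rule (Protocol 7.3.2.4); paired test (SAP 6.6(6)).

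**Assumptions not in the documents.** All 86 subjects have both values. Pre- and post-dose values are bivariate normal with equal means and SDs (no drug effect). Correlation ρ is 0.7, with 0.5 and 0.8 as the range. The share u of values beyond the abnormal limit is 2.5%, 5%, 10% or 20%.

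**Nominal level first.** If every pair is recorded, simulated rejection is 4.8% (ρ = 0.5) and 5.1% (ρ = 0.8), with mean shift 0.00 SD. This reproduces the nominal 5%.

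**Spurious shift, one-directional limit c.** For pairs kept because the post-dose value is abnormal, the expected change is (1 − ρ)·φ(c)/u. For pairs newly abnormal (abnormal after, normal before), it is (1 − ρ)·φ(c)/P(new), because pairs abnormal at both times contribute zero on average by symmetry. At ρ = 0.7 and u = 10%: φ(c) = 0.1755 and P(new) = 0.0532.
- Abnormal post-dose: 0.3 × 0.1755 / 0.10 = 0.53 SD.
- Newly abnormal: 0.3 × 0.1755 / 0.0532 = 0.99 SD.
- Expected newly abnormal pairs: 86 × 0.0532 = 4.6.

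**Newly abnormal selection, ρ = 0.7, N = 86** (200,000 simulated datasets per row; overall rejection counts datasets with fewer than two pairs as non-rejections):

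| u | mean pairs per item | shift (SD) | datasets with ≥ 2 pairs | overall rejection |
|---|---|---|---|---|
| 2.5% | 1.4 | +1.05 | 42% | 14% |
| 5% | 2.6 | +1.02 | 74% | 36% |
| 10% | 4.6 | +0.99 | 95% | 71% |
| 20% | 7.5 | +0.96 | 99.6% | 94% |

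The 36% reached 38% in some runs of 2,000 datasets.

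**Range over correlation.** Overall rejection across the same four rates runs from 19% to 99% at ρ = 0.5 (shift +1.24 to +1.43 SD) and from 10% to 87% at ρ = 0.8 (shift +0.79 to +0.83 SD).

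**Where the problem disappears.** If a pair is kept when abnormal at either time, the shift is about 0 and rejection, when the test can be run, is 5% to 8%. If abnormalities fall equally high and low, the shift is about 0 under every selection rule and rejection is about 4% to 9%.

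The Wilcoxon test uses the same selected pairs, so choosing it does not remove the selection.

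**The case against.** Four points can be made for the plan.

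**The test may seldom run.** With a limit at 1.96 SD and 86 subjects, only about 2.1 post-dose abnormal pairs (86 × 0.025 = 2.15) or 1.4 newly abnormal pairs per item are expected. At correlation 0.7, just 63% or 43% of datasets have two or more pairs. A reader might fix the number of pairs at 5 or 10 and quote rejection of 95% (5 pairs, newly abnormal) or 78% (10 pairs, abnormal post-dose). Under that limit, five newly abnormal pairs arise in about 1.5% of datasets and ten post-dose abnormal pairs in about 0.006%. Testing is also optional, so real counts could be lower. This stands: the condition in SAP 6.6(6) has some force. But it sets no minimum number of pairs and does not exclude selected pairs, and the mean change is biased even where the test does not reject.

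**The recording sentence does not say post-dose.** Read alone, it could mean abnormal at either time, which leaves the mean unbiased. This stands too. The bias comes from the after-versus-before condition in the same section, and in the text available it is not certain which entries that condition controls.

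**The form may capture everything.** A reader might infer that normal results, including negative inhibitor assays, are not recorded and that the number tested per item is unknown. The documents do not support stating this as fact. The case report form is not among them, Protocol 7.2.5.1 and SAP 4.6(2) list full panels, and the tested/not-tested mark may or may not be per item. What remains is that these sections need reconciling.

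**The stakes are limited.** This is a conditional secondary analysis in a single-arm descriptive study, and no stated decision rests on it. That limits the weight of the point but does not make the test valid.

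**Conclusion.** The point holds conditionally. Two conditions are needed: pairs are retained because of abnormality after dosing relative to before, and the item's abnormality runs mainly one way. Under both, newly abnormal selection at correlation 0.7 produces a spurious shift of about 1 SD and overall rejection from about 14% to 94% over abnormality rates of 2.5% to 20%, where 5% is intended. Correlation, abnormality rates, normality and complete testing of 86 subjects are all assumptions.

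It would go too far to say that the tests will find a shift for every item, or that they will always be computable. Without either condition rejection stays near 5% to 9%, and at low abnormality rates many items will have fewer than two pairs. The firm finding is that SAP 6.6(6) specifies a test whose validity depends on a recording rule it never addresses, while Protocol 7.7.2.1 describes a narrower and differently selected comparison. It should be corrected; confidence is moderate.

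**What to change.** Reconcile Protocol 7.3.2.4 with Protocol 7.2.5.1, SAP 4.6(2) and SAP 6.6(6). State that, for every SAP 4.6(2) item actually tested in routine care, all available pre- and post-dose values are abstracted whether normal or abnormal, with a tested/not-tested flag for each item. At minimum, do this for the inhibitor assay, so that the primary objective has a denominator. Align Protocol 7.7.2.1 with the SAP.

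If that is not done, delete the paired test from SAP 6.6(6) and report clinically significant abnormalities over the number tested for each item. Where that number cannot be recovered, list the abnormalities without percentages.

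Cost: the first option means more chart entry for about 95 subjects and no new procedures. Protocol 4 gives 30 September 2017 as the end of data collection, so it would mean returning to the charts if the form did not already hold normal values. Deleting the test costs nothing.

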7.3.3. Efficacy variables

- On-demand treatment
 - Responses to all the injection of the Xyntha Solofuse prefilled syringe used to treat bleeding (4 point scale: excellent, good, moderate, and no response)
 - Number of observations of less than expected therapeutic effect (LETE) (LETE: “no response” rated after each infusion of 2 consecutive infusions within 24 hours after on-demand treatment)
 - In case of bleeding: The number of infusions of Xyntha Solofuse prefilled syringes used to treat each new bleeding episode is rated.
 - Mean infusion dosage
- Prophylactic Therapy
 - Percentage of the study subjects who have experienced bleeding (overall, spontaneous)
 - Annualized bleeding rates (ABRs)
 - Number of observations of less than expected therapeutic effect (LETE)

(LETE: Atypical bleeding occurring within 48 hours after administration of the Xyntha Solofuse Prefilled Syringe by dosage for the prevention of bleeding (spontaneous/at traumatic))

- Mean infusion dosage
- Total factor consumption
- If the data are adequate, sub-analysis can be performed for each factor that is considered to affect the efficacy.

7.3.4. Efficacy Evaluation

On-demand treatment (surgery and bleeding)

The study subjects (or caregivers) will be given a general explanation on keeping a diary during the routine treatment situation for the purpose of clinical use. The investigator prepares medical data based on the diary written by the patient. The case report form will

be prepared based on these. For efficacy, data rated on a 4-point rating scale of “excellent”, “good”, “moderate” or “no response” will be collected retrospectively based on the criteria below:

- *Excellent*: Definite pain relief and/or improvement in signs of bleeding starting within 8 hours after an infusion, with no additional infusion administered. Point = 1.
- *Good*: Definite pain relief and/or improvement in signs of bleeding starting within 8 hours after an infusion, with at least one additional infusion administered for complete resolution of the bleeding episode.

Or,

Definite pain relief and/or improvement in signs of bleeding starting after 8 hours after an infusion, with no additional infusion administered. Point = 2.

- *Moderate*: Probable or slight improvement starting after 8 hours following the infusion, with at least one additional infusion administered for complete resolution of the bleeding episode. Point = 3.
- *No Response*: No improvement at all between infusions or during the 24 hour interval following an infusion, or condition worsens. Point = 4.

For efficacy of each infusion of the Xyntha Solofuse prefilled syringe in on-demand treatment, data rated 24 hours after the infusion or immediately before the next infusion are collected retrospectively.

Prophylactic Therapy

The study subjects (or caregivers) will be given a general explanation on keeping a diary during the routine treatment situation for the purpose of clinical use. The investigator prepares medical data based on the diary written by the patient. The case report form will be prepared based on these. Rating data of details on atypical bleeding occurring within 48 hours from administration of the Xyntha Solofuse prefilled syringe by dosage for the prevention of bleeding (spontaneous/at traumatic) are rated and collected retrospectively. (Namely, “occurred” or “not occurred” and the number of bleeding episodes if “occurred”).

7.4. Data Sources

7.4.1. Case report forms

The investigator will review the source documents and complete the electronic CRF for each study subject included. The completed original CRFs are the sole property of Pfizer and shall not be made available in any form to third parties, except for the authorized representatives of Pfizer or the appropriate regulatory authorities, without written permission from Pfizer.

The investigator has ultimate responsibility for the collection and reporting of all clinical, safety, and laboratory data entered on the CRFs, and must ensure accuracy, authenticity/originality, attributability, completeness, consistency, legibility, timeliness (contemporaneity), sustainability, and availability upon request. The CRFs must be signed by

the investigator or an authorized staff member to attest that the data contained on the CRFs is true. Any corrections to entries on the CRFs must be dated, initialed and explained (if necessary) and should not obscure the original entries.

In most cases, the source document is the hospital or doctor's study subject chart. In this case, data collected on the CRFs must match the data in this chart.

7.4.2. Record Retention

To enable evaluations and/or audits from the regulatory authorities or Pfizer, the investigator should agree to keep records, including the identity of all participating subject subjects (sufficient information associated with records, e.g. CRFs and hospital records), copy of all CRFs, SAE forms, records such as source documents, and detailed records of treatment disposition, and adequate documentation of relevant correspondences (e.g. letters, meeting minutes, telephone calls reports). The records should be retained by the investigator according to the local regulations, or as specified in the Clinical Study Agreement (whichever is longer).

If the investigator becomes unable for any reason to continue to retain study records for the required period (e.g. retirement, transfer), Pfizer should be notified beforehand. The study records must be transferred to a representative approved by Pfizer, such as another investigator, another institution, or to an independent third party arranged by Pfizer. The investigator must obtain Pfizer's written permission before disposing of any records, even if retention requirements are met.

7.5. Study Size

The calculation of sample size is not applicable for this study. At least 600 study subjects will be enrolled in this study to meet the MFDS requirements. In this study, 14 sites conduct complete enumeration study data collection for more than 86 subjects who administered this drug during study period .

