5. RATIONALE AND BACKGROUND

Xyntha Solofuse prefilled syringe was approved on March 31, 2014 in Korea. The Xyntha Solofuse prefilled syringe is administered by intravenous infusion after reconstitution of the freeze-dried powder with the diluent (0.9% Sodium Chloride). This drug consists of the identical ingredients with the previous Xyntha injection, and the drug and the diluent are supplied within the prefilled dual-chamber syringe. As required for all new drugs approved by the Ministry of Food and Drug Safety (MFDS), information on the safety and efficacy of the new drug should be provided based on the study conducted with at least 600 study subjects who are administered this drug in the setting of routine practice for 4 years from the approval date (March 31, 2014 - March 30, 2018). This non-interventional post-marketing surveillance (PMS) study is an obligation to the MFDS. However, it is expected that about 95 subjects who received this drug should be recruited and registered as study subjects. Considering the number of subjects who meet the analysis exclusion criteria, safety and efficacy information for at least 86 subjects will be collected for all subjects who received this drug during the study period. Background information on Xyntha Solofuse prefilled syringe can be obtained from the current version of the local product document, which is the single reference safety document (SRSD) for information relating to the Xyntha Solofuse prefilled syringe in this study.

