7.9. Strength and Limitations of the Study Methods

Strength:

- This is a non-interventional study to observe the safety and efficacy of the study drug under the actual condition of use.

Limitations:

- This is a study mandated by the regulatory authority to maintain approval.
- SAP and the number of study subjects to be enrolled will be decided, not by specific diseases and/or characteristics of the drug, but by the guidelines for the re-examination of new drugs etc. by the Ministry of Food and Drug Safety.

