Xyntha Solofuse prefilled syringe was approved on March 31, 2014 in Korea. The Xyntha Solofuse prefilled syringe is administered by intravenous infusion after reconstitution of the freeze-dried powder with the diluent (0.9% Sodium Chloride). This drug consists of the identical ingredients with the previous Xyntha injection, and the drug and the diluent are supplied within the prefilled dual-chamber syringe. As required for all new drugs approved by the Ministry of Food and Drug Safety (MFDS), information on the safety and efficacy of the new drug should be provided based on the study conducted with at least 600 study subjects who are administered this drug in the setting of routine practice for 4 years from the approval date (March 31, 2014 - March 30, 2018). This non-interventional post-marketing surveillance (PMS) study is an obligation to the MFDS. Although 600 is the assigned number of study subjects, the number of cases will be adjusted considering the actual number of enrolled subjects after the study start day. Background information on Xyntha Solofuse prefilled syringe can be obtained from the current version of the local product document, which is the single reference safety document (SRSD) for information relating to the Xyntha Solofuse prefilled syringe in this study.

2. Study objective(s) and Others

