2.4. Sample size Considerations

The calculation of sample size is not applicable for this study. At least 600 study subjects will be enrolled in this study to meet the MFDS requirements. Although 600 is the assigned number of study subjects, the number of cases will be adjusted considering the actual number of enrolled subjects after the study start day.

Statistical Analysis Plan for rPMS

3. Analysis Populations

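### Protocol 7.5 and SAP 2.4 still state an enrolment of at least 600, while the protocol itself expects about 95 registered and at least 86 with data; the SAP gives no replacement figure

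*Protocol*

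**What the plan says.** Protocol 7.5 disclaims any sample size calculation and then states "At least 600 study subjects will be enrolled in this study to meet the MFDS requirements". Its next sentence has 14 sites carrying out "complete enumeration study data collection for more than 86 subjects who administered this drug during study period".

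Protocol section 5 presents 600 differently. There it is what the regulator (MFDS) asks of new drugs: information "based on the study conducted with at least 600 study subjects who are administered this drug". The text then turns, with a contrasting conjunction, to the actual expectation: "it is expected that about 95 subjects who received this drug should be recruited and registered as study subjects". After an allowance for exclusions from analysis, the commitment is this: "safety and efficacy information for at least 86 subjects will be collected for all subjects who received this drug during the study period".

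SAP 2.4 carries the same 600-enrolment sentence as Protocol 7.5. Both SAP 2.4 and the SAP background add a qualification: "Although 600 is the assigned number of study subjects, the number of cases will be adjusted considering the actual number of enrolled subjects". No adjusted number follows in either place, or anywhere else in the SAP.

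Protocol 7.9 lists as a limitation that "the number of study subjects to be enrolled will be decided, not by specific diseases and/or characteristics of the drug, but by the guidelines" of the MFDS. It does not say that the expected number falls far below 600.

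**The concern.** Two incompatible sizes stand in the current text. Section 5 is coherent by itself, because it separates the requirement (600) from the expectation (95, then 86). Section 7.5 is not, because it states 600 as the number that will be enrolled and then describes a complete count of a population slightly above 86. Under complete enumeration every treated patient at the 14 sites is already counted, so those sites hold no further pool from which to reach 600.

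The SAP has the larger gap. Someone reading it alone sees 600, is told that it will change, and cannot find out to what. That matters for judging the plan's content. SAP 6.6 and 6.7 commit to logistic regression on sex, age group, disease status, renal/hepatic status and concomitant treatment, and whether such models are feasible looks very different at 600 and at 86.

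The main stake is the primary objective, detection of factor VIII inhibitor. What a study can say about an uncommon event depends mostly on how many subjects it observes.

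**Working it through.** **Inputs**
- Stated enrolment: at least 600 (Protocol 7.5; SAP 2.4).
- Expected registered: about 95 (Protocol 5).
- Expected with safety and efficacy data: at least 86 (Protocol 5); more than 86 (Protocol 7.5).
- Inhibitor rate: none given in the documents, so a range of 0.5% to 3% is assumed.

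The 600 is a regulatory number with no alpha, power or effect size behind it, so there is no calculation to reproduce. The checks are whether the stated numbers agree and what the difference means.

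**Agreement of the numbers**
- 600/95 = 6.3; 95/600 = 15.8%.
- 600/86 = 7.0; 86/600 = 14.3%.
- 95 − 86 = 9 exclusions; 9/95 = 9.5%. Conversely, 86/(1 − 0.10) = 95.6, which rounds up to 96, so the pair 95 and 86 fits an allowance of roughly 10%.

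The two lower figures agree with each other. The 600 is the outlier.

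**Zero-event upper limit.** With no inhibitor cases among n subjects, the exact two-sided 95% upper limit is 1 − 0.025^(1/n).

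**Chance of seeing at least one case** at true rate p is 1 − (1 − p)^n.

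| n | Upper limit, 0 cases | p = 0.5% | p = 1% | p = 2% | p = 3% |
|---|---|---|---|---|---|
| 600 | 0.61% | 95.1% | 99.8% | >99.9% | >99.9% |
| 95 | 3.8% | 37.9% | 61.5% | 85.3% | 94.5% |
| 86 | 4.2% | 35.0% | 57.9% | 82.4% | 92.7% |

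**Like-for-like comparison.** The 600 and 95 are counts before exclusions, and 86 is a count after them. Applying the same 86/95 retention to 600 gives 600 × 86/95 = 543. This is an illustration and does not appear in the documents. At 543 the upper limit is 0.68%, against 4.2% at 86, and the chance of at least one case at a 1% rate is 99.6%, against 57.9%. Compared before or after exclusions, the upper limit is about 6.2 times higher at the expected size (3.81/0.613; 4.20/0.677).

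All these limits assume that inhibitor status is known for every subject. Protocol 7.3.2.4 does not require laboratory tests, so they are best cases.

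**The case against.** The strongest reply is that the smaller size is already disclosed. Section 5 of the protocol states it plainly, 7.5 gives the enumeration figure in the sentence after the 600, Amendment 4 was made to adjust the target number, and the SAP warns twice that 600 will change. A careful protocol reader is not misled, and what remains is one unreconciled sentence in each document. That stands as far as the protocol goes, and it limits the weight of the point. It does not make the sentence in 7.5 correct, and it does not help the SAP, where a promised adjustment without a number is not a stated size.

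It can also be said that no sample size calculation is claimed, so this is a textual inconsistency and not failed arithmetic. That is fair. The figures in the table measure the consequence of the inconsistency and do not show an error in a calculation.

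The SAP may have been written before Amendment 4 (16 October 2017); its date is not in the text reviewed. That could explain the mismatch, but the SAP would still need aligning.

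The difference between at least 86 and more than 86 is one subject and has no analytic effect. It is worth tidying only because the same sentence has to be edited anyway.

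Finally, the documents do not show whether the MFDS accepted the lower number. That is a real gap, and the corrected text should state the position.

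**Conclusion.** The point holds. Protocol 7.5 and SAP 2.4 state an enrolment about 6.3 times what the protocol expects to register, and the SAP offers nothing in its place. The study is descriptive, claims no power and will report intervals on the actual n, so no estimate, analysis set or inclusion rule is affected. The effect is on how the planned size, and what it can show about inhibitors, is understood. With zero cases, the study could exclude rates above about 3.8% (n = 95) or 4.2% (n = 86), not 0.61% (n = 600). At an assumed 1% rate, the chance of seeing any case is about 58% to 62%, not 99.8%. These figures rest on complete ascertainment of inhibitor status and, for the detection probabilities, on rates the documents do not supply.

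**What to change.** - In Protocol 7.5, SAP 2.4 and the SAP background, replace the 600-enrolment statement with the protocol's own expectation: about 95 registered and at least 86 analysable, by complete enumeration at 14 sites. Mention 600 only as the MFDS requirement described in Protocol 5, and say whether the MFDS has agreed to the lower number.
- Use one wording for the lower figure in Protocol 5 and 7.5.
- Add a line to the limitations in Protocol 7.9 that about 95 subjects are expected against the 600 required.
- Optionally, state the precision for the primary objective: zero inhibitor cases would give an exact two-sided 95% upper limit of 3.8% at 95 and 4.2% at 86, provided status is known for all. If not all subjects are tested, use the number tested.

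The cost is wording, plus IRB/IEC approval of a protocol amendment where Protocol 8.3 makes that applicable. No extra patients, tests or site queries are needed. Data collection was planned to end on 30 September 2017, so the change affects how the plan and the final report read, not how the study is run. The price is that the stated size looks less favourable.
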